Study Protocol and Statistical Analysis Plan

Title of Study: The Effect of Graded Motor Imagery on Pain and Function in Individuals with Knee Osteoarthritis: a Comparative Randomized Controlled Trial NCT Number: NCT05925517 Date of Document: March 31, 2024

Table of contents

	Table of contents	
		Page number
Study Protocol		3
Objectives		3
Design		3
Methods		3
Statistical Analysis Plan		4

Study Protocol

Objectives:

The objective of this study was to investigate whether Graded Motor Imagery (GMI) shows comparable effectiveness to Transcutaneous Electrical Nerve Stimulation (TENS) in improving pain and functionality in individuals diagnosed with knee osteoarthritis (PwKOA).

Design:

A small randomized controlled trial design was conducted online at three time points: 1) baseline/pre-test, 2) post-test (after the 8-week intervention), and 3) follow-up (6-week follow-up). Data were collected by face-to-face interview method.

Participants will be randomly assigned to one of two conditions: 1) GMI or 2) TENS. One group underwent GMI treatment, while the other group received TENS therapy three times a week for 8 weeks. Additionally, both groups engaged in home-based and functional exercises.

The study was approved by the Marmara University Faculty of Medicine Clinical Research Ethics Committee (date: 02/06/2023, procedure number: 09.2023.795) and was by the ethical standards of the World Medical Association (Declaration of Helsinki).

Methods:

Sample and Recruitment. Patients diagnosed with unilateral knee osteoarthritis (KOA) were included in the study. To participate in the research, the following criteria must be met: 1) Grade II-III KOA as per the Kellgren and Lawrence classification and American College of Rheumatology (ACR) criteria, accompanied by symptoms and radiographic evidence; 2) experience moderate to severe pain rated as three or higher on the Visual Analog Scale (VAS) during activity; 3) participants must score at least 24 points on the Mini-Mental State Examination (MMSE); 4) age of the participants should be between 45 and 64 years. Patients diagnosed by an orthopedist were treated by a certified physiotherapist at Artvin State Hospital between 1 July 2023 and 31 March 2024.

Procedure. Throughout the GMI protocol, participants engaged in three weeks of lateralization, followed by three weeks of motor imagery (MI), and concluded with two weeks of mirror therapy (MT). Lateralisation training was conducted using the RecogniseTM Knee app. The four-stage program included 20 different knee images in each stage, with a viewing time of 5 seconds, progressing from easy to difficult (Basic, Vanilla, Context, and Abstract). During the MI task, subjects were instructed to mentally simulate engaging in activities such as climbing, swimming, and gardening. During the implementation of MT, a 90×60 cm² mirror is positioned between the lower extremities of seated patients. Subsequently, patients engage in active and progressive resistance exercises for the unaffected knee while maintaining the affected knee in a stationary position. As patients progressed, they engaged in active and progressive resistance exercises targeting the affected knee up to their pain threshold. Ultimately, they attained an equal range of motion (ROM) and resistance in both extremities. The TENS therapy was administered under medical supervision using the Intellect device by Chattanooga Group in Hixson, TN, and four distinct self-adhesive electrodes (5.08×5.08 cm, Uni-Patch, Wabasha, MN). The electrodes were placed in a square shape over the area of pain. Conventional TENS was used for 30 minutes at 100 Hz frequency, with a 100 µs pulse width,

and intensity kept below 10% of the motor threshold. The exercise program included warmup, core stability, pelvis and hip stability, gluteus medius strengthening, knee control and stability, knee strengthening exercises, and functional exercises. The home exercise protocol consisted of a 10-minute warm-up with walking, followed by stretches and exercises including straight leg raises, quadriceps setting, pillow squeezes, heel raises, one leg balance, step-ups, and quadriceps strengthening exercises, each performed in three sets of ten repetitions with a 3-minute rest in between sets.

Measures. All measurements were collected at baseline, after treatment, and during the 6-week follow-up for both groups. The only exceptions were sociodemographic characteristics and mental status, which were only assessed before the treatment began.

Mini-mental state examination (MMSE). The 11-question Mini-Mental State Examination (MMSE) with a maximum score of 30 was used for cognitive assessment. A score of 24-30 indicates normal cognitive function, while a score of 18-23 suggests mild dementia, and a score of 17 or lower indicates severe dementia.

Visual analog scale (VAS). Pain severity was measured using the Visual Analog Scale (VAS). Patients used a 10 cm VAS scale to indicate the severity of pain at rest, during activity, and at night, on a scale from 0 (no pain) to 10 (unbearable pain). Pain levels were categorized as 0-2 (safe), 3-5 (acceptable), and 6-10 (risky).

Pressure pain threshold (PPT). PPT was measured using an algometer model 1200–304(Push-Pull Force Gauge®, Fabrication Enterprises, Inc.). The evaluation was performed at points located 2 cm below the medial and lateral edges of the patella with patients lying on their side. The algometer applied gradual pressure until pain was reported. Each point was tested three times, and the average value was calculated. This method and device are reliable for PwKOA. **Range of motion (ROM).** Knee flexion and extension was measured in the prone position using

a digital goniometer (Baseline Evaluation Instrument® by Fabrication Enterprises, Inc.). The evaluation was conducted with the pivot point at the femur's lateral condyle. The stationary arm tracked the lateral midline of the femur, whereas the moving arm followed the fibulaThe measurements were performed three times, with a 30-second interval between tests, and the most accurate value was recorded.

Isometric muscle strength. Isometric muscle strength for knee flexors and extensors was assessed using a handheld dynamometer (MicroFET 2, Hoggan Health Industries Inc., Biometrics, The Netherlands). Measurements were taken three times with 30-second intervals in between. The average value in kilograms was recorded. Patients were positioned on the edge of the bed with an upright posture, arms crossed, and hips and knees flexed at a 90° angle. The dynamometer was placed two finger-widths above the lateral malleolus on both the anterior and posterior aspects of the tibia.

Timed up and go test (TUG). The physical performance was assessed with TUG in PwKOA by timing the process of standing up from a chair, walking along a line, turning, and sitting back down. The average time of two trials is calculated after the initial attempt.

Western Ontario and McMaster Universities osteoarthritis index (WOMAC). The assessment of pain, stiffness, and physical function was carried out using the WOMAC, which encompasses 24 items scored on a scale ranging from 0 to 4. Elevated scores are indicative of heightened disability.

Statistical Analysis Plan

Statistical analysis was performed using IBM SPSS version 22.0 software (IBM Corp., Armonk, NY, USA). Qualitative variables were expressed as frequencies and percentages, whereas quantitative variables were presented as means and standard deviations. The normality of the data distribution was evaluated using the Kolmogorov-Smirnov test. Homogeneous

numerical variables were compared using the Independent Samples T-Test, and categorical variables were analyzed using the Chi-Square Test to assess pre-treatment demographic characteristics between groups. Repeated measures ANOVA (rANOVA) was employed to compare baseline (T0), post-treatment (T1), and six-month follow-up (T2) scores, with Bonferroni post hoc analysis conducted to identify the specific sources of differences. A mixed between-within subjects analysis of variance with Tukey's post hoc test was utilized to evaluate the effects of two different treatments (GMI, TENS) across three time points (baseline, post-treatment, and six-month follow-up). In all analyses, statistical significance was set at p<0.05 (two-tailed).

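### The objective asks whether GMI is comparable to TENS, but the SAP only tests for a difference: no margin, no between-arm interval, no rule for concluding comparability

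*Combined protocol and SAP*

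**What the plan says.** The Objectives section gives one aim: to "investigate whether Graded Motor Imagery (GMI) shows comparable effectiveness to Transcutaneous Electrical Nerve Stimulation (TENS) in improving pain and functionality". The Design section describes the trial as follows: "A small randomized controlled trial design was conducted online at three time points". It adds: "Additionally, both groups engaged in home-based and functional exercises".

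The Statistical Analysis Plan contains three kinds of inferential analysis:

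- t-tests and chi-square tests, for pre-treatment characteristics;
- a repeated measures ANOVA with Bonferroni comparisons, for the three time points;
- a mixed between-within ANOVA, which "was utilized to evaluate the effects of two different treatments (GMI, TENS) across three time points".

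One criterion covers them all: "In all analyses, statistical significance was set at p<0.05 (two-tailed". Planned summaries are means with SDs, or frequencies with percentages. The documents give no margin, no between-arm confidence interval, no one-sided or equivalence test, and no sample size, power, SD or expected effect.

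**The concern.** Whether one treatment is comparable to another is an equivalence or non-inferiority question. It is answered by showing that any deficit is smaller than a stated amount. A difference test has the opposite structure: equality is the null hypothesis, and failing to reject it is not evidence for it. Only the mixed ANOVA compares the arms after baseline, and the SAP does not say whether its group term or its group-by-time term decides.

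The within-arm analyses cannot fill the gap. Both arms also exercise, so improvement over time in both would not show that GMI does as well as TENS.

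The document does not say how p>0.05 will be interpreted. No other written route leads to an answer, so a non-significant result could be read as comparability. That reading errs more often the smaller the trial, and this trial is described as small.

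**Working it through.** **Matching the objective to the analyses**

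| SAP element | What it compares | Can it show comparability after treatment? |
|---|---|---|
| t-test, chi-square | Arms, before treatment | No |
| Repeated measures ANOVA, Bonferroni | Time points | No |
| Mixed ANOVA, p<0.05 two-sided | Arms across T0, T1, T2 | Can detect a difference; cannot establish its absence |
| Means and SDs | Descriptive | No margin or rule attached |

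The plan has no figure of its own to reproduce. The rest illustrates, for one outcome, how often the planned test would miss a real deficit.

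**Assumed inputs (none is in the documents).** 1:1 allocation; n = 20 or 30 per arm; SD of 1 at every visit; compound symmetry with correlation ρ = 0.3, 0.5, 0.7 or 0.8; true GMI deficit of 0 at T0 and 0.5 SD at T1 and T2. From the SAP: α = 0.05, two-sided.

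**1. Group-by-time term.** Noncentral F with 2 and 2(2n − 2) df, and λ = n × Σ(δₜ − δ̄)² / [2(1 − ρ)].
- δ = (0, 0.5, 0.5) has mean 0.333, so Σ(δₜ − δ̄)² = 0.111 + 0.028 + 0.028 = 0.167.
- For n = 20, ρ = 0.5: λ = 20 × 0.167 / 1 = 3.33 on 2 and 76 df; P(non-significant) = 66%.

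**2. Group main effect.** This is a t-test on each person's mean over T0 to T2. Including T0 dilutes the difference to 0.333 SD; the variance of the mean is (1 + 2ρ)/3.
- For n = 20, ρ = 0.5: SE = √(2/20 × 0.667) = 0.258; noncentrality 0.333/0.258 = 1.29; P(non-significant) = 76%.

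**3. Unadjusted t-test at one visit.** Noncentrality 0.5 × √(n/2), which is 1.58 at n = 20.

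Probability of p>0.05 despite the 0.5 SD deficit:

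| Test | n per arm | ρ=0.3 | 0.5 | 0.7 | 0.8 |
|---|---|---|---|---|---|
| Group-by-time | 20 | 75% | 66% | 47% | 28% |
| Group-by-time | 30 | 63% | 51% | 28% | 11% |
| Group main effect | 20 | 71% | 76% | 79% | 80% |
| Group main effect | 30 | 59% | 66% | 71% | 72% |
| t-test, one visit | 20 | 66% | 66% | 66% | 66% |
| t-test, one visit | 30 | 52% | 52% | 52% | 52% |

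The group-by-time figures are 80/74/59/42% at n = 15 and 43/27/8/1% at n = 50. Higher correlation helps this term and hurts the main effect, so the unstated choice of term matters.

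**4. A rule that does address comparability.** Two one-sided tests at 5% each on the baseline-adjusted T1 difference, with an assumed margin of 0.5 SD (simulation, 20,000 trials per cell). Probability of concluding comparability:

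| True deficit | n per arm | ρ=0.3 | 0.5 | 0.7 | 0.8 |
|---|---|---|---|---|---|
| 0.5 SD (wrong conclusion) | 20 | 1.5% | 2.8% | 4.8% | 5.0% |
| 0.5 SD (wrong conclusion) | 30 | 4.2% | 4.4% | 4.9% | 5.2% |
| 0 (right conclusion) | 20 | 4.5% | 12.4% | 38.4% | 63.4% |
| 0 (right conclusion) | 30 | 27.0% | 41.3% | 68.4% | 87.3% |

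The error of about 5% or less holds by construction, because the margin equals the true deficit. The last two rows show what that control costs in a small trial.

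**5. Precision.** The unadjusted 90% CI half-width is t(0.95, 2n − 2) × √(2/n): 1.686 × 0.316 = 0.53 SD at n = 20, and 0.43 SD at n = 30. Baseline adjustment, t(0.95, 2n − 3) × √[2(1 − ρ²)/n], gives 0.51/0.46/0.38/0.32 SD and 0.41/0.37/0.31/0.26 SD across the four correlations.

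**The case against.** The strongest reply is that 'comparable' is loose wording. The documents never mention equivalence or non-inferiority, the title calls the trial comparative, and the SAP speaks of evaluating the effects of two treatments. If the question is simply how GMI compares with TENS, the mixed ANOVA addresses it. That reading is possible but not the natural one, since the objective asks whether GMI shows comparable effectiveness. It would also still require the objective to be reworded, and p>0.05 still could not be reported as comparability.

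Second, the document nowhere says it will treat non-significance as comparability. That stands: the certain defect is the missing margin and rule, and the error rates describe a misreading the plan leaves open.

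Third, every number above is assumed, and the miss rate falls to 1% at 50 per arm with correlation 0.8. That also stands. The figures show direction and plausible size, not the error rate of this trial.

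Fourth, if means, SDs and numbers are reported by arm and visit, a reader could compute an unadjusted interval. That would still supply neither margin nor rule.

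**Conclusion.** The concern holds. Followed exactly, the plan cannot answer its only objective, because the sole post-baseline comparison of the arms is a test of difference. This conclusion comes from the text and needs no assumed number.

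The size is illustrative. With a true deficit of 0.5 SD and 20 to 30 per arm, non-significance would occur in 11% to 80% of trials, depending on the correlation and on which ANOVA term is read. Without a margin, nothing in the plan limits the chance of wrongly calling GMI comparable. Because the headline conclusion depends on this, it must be corrected before results are interpreted.

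**What to change.** **Minimum change.** For each outcome, report GMI minus TENS with its 95% CI, preferably baseline-adjusted. State that p>0.05 alone means no difference was detected and is inconclusive. This costs only text and intervals from measurements the plan already collects.

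**Then choose one of two routes.**

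1. *Keep the comparability claim.*
   - Restrict it to one named pain or function outcome at one named time point. If it is to cover both pain and function, name one of each and require both to pass.
   - Activity VAS at T1 is a candidate: it is the only outcome measure used in the entry criteria, and T1 is timed consistently. T2 is six weeks in the Design and Measures text, but the SAP has "post-treatment (T1), and six-month follow-up (T2) scores"; those passages must be reconciled.
   - Conclude equivalence only if the 90% CI (two one-sided tests at 5%) lies within a justified margin fixed before the arms are compared. If non-inferiority is meant, use the one-sided bound and state its level; one-sided 0.025 matches the SAP's two-sided 0.05.
2. *If no margin can be justified,* reword the objective as estimating the difference between GMI and TENS. This costs one sentence.

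**Timing.** The document carries "Date of Document: March 31, 2024", the last day of the treatment period given as "between 1 July 2023 and 31 March 2024". An 8-week course begun by 4 February 2024 (31 March minus 56 days) would have ended by then. Any margin set after outcome data were seen must be labelled post hoc.

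**Downside.** A margin needs clinical justification, and the result may have to be called inconclusive: even with no true difference, the 0.5 SD rule illustrated above would succeed in only about 5% to 63% of trials at 20 per arm.

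### The GMI-TENS comparison makes no use of Kellgren-Lawrence grade, which is determined at entry; adjusting for it would be a cheap safeguard against chance imbalance in a small trial.

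*Combined protocol and SAP*

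**What the plan says.** Four statements bear on the point.

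- **Eligibility** (Study Protocol, Methods, Sample and Recruitment): patients must have "Grade II-III KOA as per the Kellgren and Lawrence classification". Grade is not mentioned again under Design, Measures or the Statistical Analysis Plan.
- **Allocation and size** (Study Protocol, Design): "Participants will be randomly assigned to one of two conditions: 1) GMI or 2) TENS". No stratification, blocking or minimisation is described. On size the text says only "A small randomized controlled trial design was conducted"; no number of patients is stated.
- **Baseline tests** (Statistical Analysis Plan): "numerical variables were compared using the Independent Samples T-Test", and "categorical variables were analyzed using the Chi-Square Test to assess pre-treatment demographic characteristics between groups". The two-sided 0.05 level applies to all analyses. The variables tested are not listed, and no action is attached to the results.
- **Between-arm analysis** (Statistical Analysis Plan): a mixed between-within ANOVA "was utilized to evaluate the effects of two different treatments (GMI, TENS) across three time points". Baseline (T0) is one of the three time points. No covariate is named.

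**The concern.** If radiographic grade predicts how much a patient improves, an arm that receives more grade III knees by chance will look worse, or less improved, for reasons unrelated to treatment. Stratified allocation would limit this at the design stage, and covariate adjustment would correct for it in the analysis. The plan describes neither, although the variable is already available from the eligibility assessment.

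The baseline tests do not fill the gap. Under random allocation any baseline difference is due to chance, so a significant result is a false alarm about the hypothesis tested. In a small trial a non-significant result does not show balance. In any case, neither result changes the GMI-TENS estimate.

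Two things are at stake: how accurate the single observed contrast is, given whatever grade split occurs, and some precision.

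**Working it through.** The plan gives no sample size, power or effect size, so there is no stated figure to reproduce. The calculation below is an illustration.

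**Inputs**

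- From the documents: two randomised arms, two-sided 0.05 level, grade II or III at entry.
- Assumed: equal arms of n = 15 to 40, half of patients grade III, simple randomisation, and a grade III versus II effect on change from T0 of g = 0.3 to 0.8 SD, where SD is the within-grade SD of change.

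**Step 1. How often a sizeable gap arises, and whether a test would flag it.** The numbers of grade III patients in the two arms are independent Binomial(n, 0.5). Sum the joint probability over all pairs whose proportions differ by at least 0.20, then over those pairs that also reach p<0.05 on an uncorrected chi-square test.

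| n per arm | P(gap of 20 points or more) | of which flagged | unflagged share |
|---|---|---|---|
| 15 | 36.2% | 4.6% | 1 − 4.6/36.2 = 87% |
| 20 | 26.8% | 4.3% | 1 − 4.3/26.8 = 84% |
| 30 | 15.5% | 5.2% | 1 − 5.2/15.5 = 66% |
| 40 | 9.3% | 5.7% | 1 − 5.7/9.3 = 39% |

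At 20 per arm the smallest split near one half that reaches p<0.05 is 13 versus 6, a 35-point gap. So even if grade is among the variables tested, most gaps of 20 points or more would pass at 20 to 30 per arm.

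**Step 2. Size of the shift.** Shift = gap × g.

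- g = 0.3: 0.20 × 0.3 = 0.06 SD.
- g = 0.8: 0.20 × 0.8 = 0.16 SD.

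The standard error of the contrast is √(2/n) SD. At 20 per arm that is 0.316, so the shift is 0.06/0.316 = 0.19 to 0.16/0.316 = 0.51 standard errors.

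**Step 3. Type I error given a 20-point gap.** The unadjusted test uses a within-arm variance of 1 + 0.24g² (a 40:60 split gives 0.4 × 0.6 = 0.24), so its critical value is c = 1.96 × √(1 + 0.24g²) × √(2/n). The contrast is centred on 0.20g with standard error √(2/n). Under the normal approximation, with g from 0.3 to 0.8:

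- 20 per arm: 5.2% to 5.9%.
- 30 per arm: 5.4% to 7.2%.
- 40 per arm: 5.6% to 8.5%.

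These rates apply only to trials with such a gap. Over all randomisations the rate is the nominal 5%.

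**Step 4. Precision gained by adjusting.** With half the patients grade III, the unadjusted variance is 1 + g²/4. Adjustment reduces it to 1, at a cost factor of about 1 + 1/(2n − 4) for estimating the grade effect. Net reduction = 1 − [1 + 1/(2n − 4)]/(1 + g²/4).

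- 20 per arm, g = 0.3: 1 − 1.0278/1.0225 = −0.5%.
- 20 per arm, g = 0.8: 1 − 1.0278/1.16 = 11.4%.
- 40 per arm, g = 0.3: 1 − 1.0132/1.0225 = 0.9%.
- 40 per arm, g = 0.8: 1 − 1.0132/1.16 = 12.7%.

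The gain therefore runs from about nil to 13%. If grade has no effect on change, the cost at 20 per arm is a 2.8% increase in variance.

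**The case against.** The case against has five parts, and much of it stands.

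- **The baseline tests change nothing.** No covariate selection, exclusion or change of model depends on them. This is correct: removing them alters no estimate or error rate. A reader might infer that they threaten the trial's validity, or point out that running many of them makes a spurious p<0.05 likely. The documents do not say how many are run, and a spurious result would have no consequence in the plan.
- **The plan may already check grade.** A reader might infer that grade goes untested, or that the plan will declare the arms comparable. Neither is in the text. The tested variables are described as demographic but not listed, and no declaration of comparability is planned. Testing grade would still not bring it into the treatment comparison.
- **Baseline severity is already handled.** T0 is a level of the time factor, so the group-by-time term compares changes from baseline. If grade only reflects a worse starting score, its effect cancels. This is correct, and it is why the calculation concerns the effect of grade on change. The documents give no figure for that effect.
- **The unadjusted contrast is valid.** It is, on average over randomisations. What remains is the shift in the one trial run, and the precision forgone.
- **Grade is one candidate among several.** This also stands. The reason to pick it is practical: the eligibility criteria already require it, and it has only two levels.

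**Conclusion.** The point holds as a cheap improvement to the analysis. It is not a validity failure. The GMI-TENS model leaves out a baseline variable that is determined at entry and could be prognostic, and in a small trial an appreciable imbalance in it is quite likely: about 27% of trials at 20 per arm and 16% at 30 per arm for a gap of 20 points or more. The resulting shift, 0.06 to 0.16 SD, is modest.

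That grade is determined for each patient follows from the eligibility criterion. The arm sizes, the equal split of grades and the 0.3 to 0.8 SD effect on change are assumptions. If grade does not predict change, nothing is gained and almost nothing is lost. A reader might go further and conclude that the unadjusted comparison is biased or its error rate uncontrolled; the documents do not support that for a randomised comparison.

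**What to change.** Add KL grade (II versus III) as a fixed covariate, with its interaction with time, to every GMI-TENS comparison, whatever imbalance is observed. The interaction is needed because a grade main effect alone shifts all three time points equally and leaves the comparison of changes unadjusted.

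Replace the baseline p-values with a descriptive table by arm showing demographics, KL grade and T0 scores. This affects reporting only.

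Timing matters. The document is dated 31 March 2024, the last day of the stated treatment period, and is largely in the past tense. If outcome data had been examined before the covariate is added, report the adjusted model as a later-added sensitivity analysis beside the planned one.

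Cost: SAP wording and about one degree of freedom per contrast, with no new data beyond the grade established at entry. At 20 per arm there is little or no precision gain if the grade effect on change is only about 0.3 SD.

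### The only between-group outcome analysis is a mixed ANOVA with baseline as an outcome level; it plans no GMI minus TENS difference or confidence interval and no baseline adjustment

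*Combined protocol and SAP*

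**What the plan says.** The objective is to learn "whether Graded Motor Imagery (GMI) shows comparable effectiveness to Transcutaneous Electrical Nerve Stimulation (TENS) in improving pain and functionality" (Study Protocol, Objectives). The design is a two-arm randomised trial: "Participants will be randomly assigned to one of two conditions: 1) GMI or 2) TENS" (Design). Outcomes are measured three times: "All measurements were collected at baseline, after treatment, and during the 6-week follow-up for both groups" (Methods, Measures).

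The Statistical Analysis Plan lists these inferential procedures:

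- A t test and a chi-square test, used "to assess pre-treatment demographic characteristics between groups".
- A repeated measures ANOVA comparing T0, T1 and T2, "with Bonferroni post hoc analysis conducted to identify the specific sources of differences". No treatment factor is named.
- For the arms: "A mixed between-within subjects analysis of variance with Tukey's post hoc test was utilized to evaluate the effects of two different treatments", "across three time points (baseline, post-treatment, and six-month follow-up").

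Significance is two-sided at 0.05. Quantitative variables are summarised by means and SDs.

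**The concern.** Only the mixed ANOVA compares GMI with TENS on outcomes, and it leaves four things open.

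1. It does not name the term that carries the treatment comparison. The group-by-time interaction is the natural reading, but it is an omnibus test with 2 degrees of freedom and yields no difference or interval at T1 or T2.
2. The post hoc tests do not fill the gap. Bonferroni belongs to the comparison of time points, and Tukey's test has no stated target.
3. Each outcome's baseline value is collected but enters as a level of the response, not as a covariate, which costs precision.
4. If the group main effect were read as the treatment effect, it would include the baseline visit, where randomised arms are expected to be equal.

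The objective makes this matter. Whether two treatments are comparable depends on how large a difference the data still allow at a stated time. An F test, significant or not, does not answer that. In a trial the protocol itself describes as small, a non-significant F could be misread as comparability.

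**Working it through.** The plan has no figure to reproduce: it states no sample size, SD, effect size, correlation or margin. All inputs here are therefore assumptions: n = 25 per arm, SD = 1, compound symmetry with correlation rho between visits, and a true difference d = 0.8 SD where power is shown.

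**What the interaction test can tell apart.** Its noncentrality is lambda = (n/2) × (sum of squared centred arm differences over T0, T1, T2) / (1 − rho). Four patterns of arm difference give the same sum:

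- (0, d, d), (0, d, 0) and (0, 0, d): (2/3)d² = (2/3)(0.64) = 0.427.
- (0, e, −e) with e = d/√3 = 0.462: 2e² = 0.427.

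At rho = 0.5, lambda = 12.5 × 0.427 / 0.5 = 10.67 for all four, and power is 83% (noncentral F, 2 and 96 df). A lead for GMI at both times, a lead at one time only, and a lead followed by an equal deficit are all equally likely to produce a significant result.

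**Precision at T1.** The variance of the arm difference is:

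- baseline-adjusted: (2/n)(1 − rho²), 47 df;
- change from baseline: (2/n) × 2(1 − rho), 48 df;
- unadjusted T1 values: 2/n, 48 df.

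Adjusted over change is (1 − rho²) / [2(1 − rho)] = (1 + rho)/2, below 1 for any rho below 1. Adjusted over unadjusted is 1 − rho², below 1 unless rho = 0. Neither ratio depends on n. At rho = 0.5 the adjusted half-width is 2.012 × √(0.08 × 0.75) = 2.012 × 0.245 = 0.49, and the change-score half-width is 2.011 × √(0.08 × 1) = 2.011 × 0.283 = 0.57.

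The table gives 95% CI half-widths in SD units, then power for d = 0.8.

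| rho | Adjusted | Change | Unadjusted | Power: adjusted T1, alpha 0.05 | Power: adjusted, alpha 0.025 | Power: interaction |
|---|---|---|---|---|---|---|
| 0.3 | 0.54 | 0.67 | 0.57 | 83% | 74% | 68% |
| 0.4 | 0.52 | 0.62 | 0.57 | 86% | 78% | 75% |
| 0.5 | 0.49 | 0.57 | 0.57 | 89% | 82.6% | 82.9% |
| 0.6 | 0.46 | 0.51 | 0.57 | 93% | 88.5% | 90.6% |
| 0.7 | 0.41 | 0.44 | 0.57 | 97% | 94.7% | 96.9% |

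The alpha 0.025 column is Bonferroni over T1 and T2. In sample-size terms, 25 per arm with adjustment is as precise as change scores with 25/0.75 = 33.3 per arm at rho = 0.5, or 25/0.85 = 29.4 at rho = 0.7. A simulation of 10,000 trials at rho = 0.5, with slope and SD estimated, agreed: interaction power 83.0%, adjusted T1 power 88.9%, mean half-widths 0.495 and 0.567.

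**Tukey's test.** With two groups and 48 df its critical value on the t scale is 2.011, the same as Student's t. On the group factor it is therefore an ordinary t test of means averaged over all three visits. For a constant effect d that average estimates (0 + d + d)/3 = (2/3)d.

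**The case against.** The interaction is a valid, undiluted test of differential change, so what remains could be called a reporting gap plus a preference among sound methods. That the analysis is valid stands, and no claim of invalidity is made here.

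Means and SDs are to be presented. If they are given by arm and visit, a reader can see timing and direction and work out an unadjusted interval. That is possible, but the plan does not promise that layout, and descriptive summaries are not a planned treatment estimate.

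The change score is not a contrast the plan names, and the unadjusted T1 difference is an equally natural benchmark. That is fair. Against it the gain at rho = 0.3 is small (0.54 against 0.57) and at rho = 0.7 larger (0.41 against 0.57). Adjustment is the more precise against either.

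The power levels depend on the assumed n and d. With d = 0.5, n = 25 and rho = 0.5, power is 52% for adjusted T1 and 42% for the interaction. With n = 15 and d = 0.8 it is 68% and 59%. If both times are tested with Bonferroni, the figures become 40% against 42% and 57% against 59%. So power is not the argument for the change, except where one time point is named.

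Tukey's test might instead be meant for the six group-by-time cells, which would include GMI against TENS at T1 and T2. The text does not say so. Under that reading those two contrasts would be corrected alongside all 6 × 5 / 2 = 15 pairs and would still ignore the baseline covariate.

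**Conclusion.** The concern holds. The plan's single between-group outcome analysis is valid if the interaction is the treatment test, but that is unstated, and no arm difference, interval or baseline adjustment is specified. This should be changed; it does not invalidate the trial.

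The main gain is an interpretable and narrower interval. Under compound symmetry, variance falls to (1 + rho)/2 of the change-score variance whatever the sample size: 0.65 at rho = 0.3, 0.75 at 0.5, 0.85 at 0.7. The half-widths rest on the assumed 25 per arm. A power gain over the interaction is clear only for one named time point and nearly vanishes by rho = 0.7. The interval alone cannot establish comparability, because no margin is stated; that is a separate gap.

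**What to change.** 1. Reconcile the follow-up time. Design has "3) follow-up (6-week follow-up") and Measures also says 6 weeks, while the Statistical Analysis Plan says six months. A T2 contrast cannot be defined until this is settled.
2. Replace the mixed ANOVA as the treatment comparison with ANCOVA at each time, or a linear mixed model on T1 and T2 with group, time, group-by-time and the outcome's baseline value. A baseline-by-time term is an optional refinement that lets the baseline slope differ between times, as separate ANCOVAs do.
3. Analyse every participant with a follow-up value in the group assigned at randomisation, and report the adjusted GMI minus TENS difference with 95% CI at T1 and T2.
4. Name one time as the main contrast. T1 is the only post-treatment time the documents define without conflict. If both times are tested with Bonferroni, expect no power gain over the interaction at rho = 0.5 and a small loss at 0.6 and 0.7.
5. Delete Tukey's test. If the mixed ANOVA is kept alongside, state that its group-by-time interaction is the treatment test.
6. Do not claim comparability from the interval without a margin.

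The cost is SAP wording and one model per outcome, in the software already named and on data already collected. The document is written in the past tense and dated March 31, 2024, the last day of the stated treatment period. If outcomes have already been analysed, the new analysis should be labelled post hoc.
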